 - If no evidence of clinically meaningful TLS, obtain TLS panel every 4 hours during the first 24 hours post end of alvocidib infusion (LDH levels are recommended to be assessed at least once every 24 hours).
 - If, after the first 24 hours post end of alvocidib infusion, there is no evidence of TLS, obtain TLS panel approximately every 6 hours for the remainder of alvocidib treatment and then every 12 hours after completion of alvocidib and during cytarabine and mitoxantrone (LDH levels are recommended to be assessed at least once every 24 hours).
 - Monitor fibrinogen levels at baseline and then as clinically indicated.
 - Patients who are determined to be at intermediate- or high-risk for TLS should be considered for rasburicase prophylaxis according to institutional standards

- *Patients randomized to CM:*
 - During the first 24 hours - Monitor tumor lysis labs at the start of cytarabine and approximately every 6 hours. Laboratory studies during this period should be run as a “STAT” to ensure the results are available in a timely manner.
 - If no evidence of TLS during the first 24 hours, then monitor tumor lysis labs every 12 hours until completion of mitoxantrone.
 - Monitor fibrinogen levels at baseline and then as clinically indicated.
- For patients **NOT at high** risk for TLS:
 - *Patients randomized to ACM (or who cross over to ACM after failure of CM):*
 - During the first 24 hours - Monitor tumor lysis labs at the start of alvocidib and approximately every 4 hours. Laboratory studies during this period should be run as a “STAT” to ensure the results are available in a timely manner (LDH levels are recommended to be assessed at least once every 24 hours).
 - If no evidence of TLS during first 24 hours, then monitor tumor lysis labs approximately every 6 hours for the remainder of alvocidib treatment and then every 12 hours after the completion of alvocidib and during cytarabine and mitoxantrone (LDH levels are recommended to be assessed at least once every 24 hours).
 - Monitor fibrinogen levels at baseline and then as clinically indicated.
 - *Patients randomized to CM:*
 - During the first 24 hours - Monitor tumor lysis labs at the start of cytarabine and approximately every 6 hours. Laboratory studies during this period should be run as a “STAT” to ensure the results are available in a timely manner.

- If no evidence of TLS during first 24 hours, then monitor tumor lysis labs every 12 hours until completion of mitoxantrone.

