Per-Protocol Population: The subset of safety patients who either (a) have at least one response assessment on study, or (b) die prior to their first scheduled response assessment; however, patients are excluded from the per-protocol population if they have an important protocol deviation, such as when evidence is found indicating they failed to meet any study inclusion/exclusion criterion (see section 7.1)

Platelet Recovery: Platelet count $\geq 100 \times 10^9/L$ following the administration of study drug

Pointwise: without controlling for multiple comparisons

Prestudy: Occurrence prior to randomization

Response-Available Population: The subset of safety patients who have at least one response assessment on study (see section 7.1)

Safety Population: The subset of intent-to-treat patients who received at least one dose of study drug (see section 7.1)

Sensitivity Analysis: study of how statistical methodology and assumptions affect results of the primary analysis

Shift Table: two-way frequency table pairing baseline value with the most extreme post-baseline result

Study Drug: alvocidib, Ara-C (cytarabine) and mitoxantrone

Supportive Analysis: synonymous with Sensitivity Analysis

Treatment Failure: failing to achieve a CR, CRi, CRp or PR following induction therapy (see section 7.9.2)

4. Introduction

This Statistical Analysis Plan (SAP) details the planned methodology for summarizing data collected in the clinical study conducted under Tolero, Inc. protocol TPI-ALV-201 and for comparing outcomes between the two treatment arms, ACM (alvocidib, Ara-C [cytarabine] and mitoxantrone) and CM (Ara-C [cytarabine] and mitoxantrone). The current version of the study protocol is Amendment 7 dated 30-MAY-2018. Future protocol amendments (if any) will be reviewed to assess whether the changes necessitate modification of this SAP.

Since the study protocol is a companion document to this SAP, aspects in the protocol unrelated to statistical issues (e.g., patient eligibility criteria, descriptions of clinical materials, and criteria for defining treatment failure, response to treatment and disease relapse) are not repeated here.

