7.11.3. Classification of Tumor Lysis Syndrome

Cairo-Bishop definitions for laboratory TLS and clinical TLS will be used to diagnose and grade TLS.¹⁴ Patients are classified as experiencing laboratory TLS if they have any two or more serum values of uric acid, potassium, phosphorus and/or calcium shown in Table 8 within 3 days before or 7 days after the initiation of study drug.

Table 8. Cairo-Bishop Definition of Laboratory Tumor Lysis Syndrome

Laboratory Parameter	Criteria
Uric Acid	≥476 μmol/L or 25% increase from baseline
Potassium	≥6.0 mmol/L or 25% increase from baseline
Phosphorus	≥1.45 mmol/L or 25% increase from baseline
Calcium	≤1.75 mmol/L or 25% decrease from baseline

Diagnosis of clinical TLS requires the presence of laboratory TLS and elevated serum creatinine levels, cardiac arrhythmia and/or seizures. Criteria for grading the severity of clinical TLS are presented in Appendix 1.

The numbers of patients experiencing laboratory TLS and the various severities of clinical TLS will be summarized within and between treatment arms.

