7.11.4. Clinical Laboratory Parameters

Typical comparisons of results summarized by visit may have limited interpretability in this study because (1) study drugs from the two treatment arms are administered on

different cycle days (Days 1-9 for ACM versus Days 1-4 for CM), (2) the schedule for clinical laboratory evaluations (cycle day and frequency) is different between the treatment arms, and (3) additional cycles of treatment start according to patients' response to treatment rather than based on a predetermined schedule. Therefore, four groups of laboratory data will be summarized separately:

- Cycle 1 results (from all patients in the safety population) up to the day a patient starts Cycle 2 or 10 weeks after starting Cycle 1, whichever comes first
- Cycle 2 results (from patients in the safety population who receive at least 2 cycles of study drug) up to the day a patient starts Cycle 3 or 10 weeks after starting Cycle 2, whichever comes first
- Cycle 3 results (from patients in the safety population who receive at least 3 cycles of study drug) up to the day a patient starts Cycle 4 or 10 weeks after starting Cycle 3, whichever comes first
- Cycle 4 results (from patients in the safety population who receive 4 cycles of study drug) up to 10 weeks after starting Cycle 4

Laboratory test results measured on a continuous scale and changes from baseline values will be summarized within treatment arm using mean, standard deviation, median, minimum and maximum values. Results will be summarized at baseline, on Days 1-9, and every 7 days starting with Day 15 for patients receiving ACM, and at baseline, on Days 1-4, and every 7 days starting with Day 8 for patients receiving CM. Up to the point of starting a new treatment cycle or withdrawing from the study, a patient's most recent test result will be carried forward and included in analyses on days when clinical laboratory testing was not performed.

Ordinal categorical test results will be summarized within treatment arm using shift tables. Additionally, for tests where CTCAE [version 4.03] severity criteria are specified, CTCAE severity grades will be summarized in shift tables.

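### Laboratory TLS is compared between arms, although the protocol schedules about twice as many chemistry panels in ACM as in CM over the TLS window

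*SAP*

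**What the plan says.** SAP section 4.1 (Table 1) lists the presence and severity of TLS as a safety endpoint. Statistical objective 4 in SAP section 4.2 says that safety in relapsed/refractory patients is judged relative to CM.

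Under SAP section 7.11.3 a patient has laboratory TLS with "any two or more serum values of uric acid, potassium, phosphorus and/or calcium" meeting the Table 8 limits "within 3 days before or 7 days after the initiation of study drug". Those limits include a 25% change from baseline. Clinical TLS requires laboratory TLS plus raised creatinine, arrhythmia or seizure. On reporting, the section says "The numbers of patients experiencing laboratory TLS and the various severities of clinical TLS will be summarized within and between treatment arms". It sets no common sampling times and does not ask for the number of panels.

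Protocol section 4.6.1.1 sets the sampling. For ACM patients not at high risk, panels are four-hourly in the first 24 h; without evidence of TLS, staff "then monitor tumor lysis labs approximately every 6 hours for the remainder of alvocidib treatment and then every 12 hours after the completion of alvocidib", continuing through cytarabine and mitoxantrone. CM panels are six-hourly in the first 24 h; without evidence of TLS, staff "then monitor tumor lysis labs every 12 hours until completion of mitoxantrone". After that, CM testing is weekly, or more often if clinically indicated (protocol section 5.4.3).

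SAP section 7.11.4 recognises that "the schedule for clinical laboratory evaluations (cycle day and frequency) is different between the treatment arms", but draws the consequence only for results summarised by visit.

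**The concern.** A rule that flags a patient on any qualifying values depends on how often one looks. With more panels, a short excursion is more likely to be caught and random variation has more chances to cross a 25% limit. A worst-value rule is more exposed to this than a by-visit mean, yet the SAP's caveat is attached to the by-visit means and not to TLS.

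TLS is a central risk in the alvocidib programme, and CM is the only control. If the table shows more laboratory TLS in ACM, the reader cannot tell how much is alvocidib and how much is sampling. The imbalance can carry into clinical TLS, which cannot be diagnosed without laboratory TLS and whose renal grade uses creatinine from the same panel.

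**Working it through.** The documents state no panel count, so there is no plan figure to reproduce. The counts below use the protocol as supplied.

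**Inputs.** Window after first dose: 7 × 24 = 168 h (SAP 7.11.3). Alvocidib is given on Days 1-3 as 30 min plus 4 h, so the last infusion ends at about 48 + 4.5 = 52.5 h (protocol 4.5.3.1). CM mitoxantrone ends at about 72 + 12 + 1 to 2 = 85 to 86 h (protocol 4.5.3.2). Sampling intervals are from protocol 4.6.1.1.

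**Step 1: panels after the start panel, patients not at high risk.**

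- ACM: 4, 8, ..., 24 h (6) + 30, 36, 42, 48 h (4) + 64.5, 76.5, ..., 160.5 h (9) = 19.
- CM: 6, 12, 18, 24 h (4) + 36, 48, 60, 72, 84 h (5) = 9.
- Hours 96 to 168: ACM 100.5, 112.5, ..., 160.5 h = 6; CM 0.

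**Step 2: other readings.**

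| Reading | ACM | CM | Ratio |
|---|---|---|---|
| As in step 1 | 19 | 9 | 2.1 |
| Start panel counted | 20 | 10 | 2.0 |
| CM Day 8 panel counted (6 vs 1 in hours 96-168) | 19 | 10 | 1.9 |
| ACM six-hourly phase run to 54 h or 72 h | 20 or 22 | 9 | 2.2 or 2.4 |
| High risk, four-hourly | 19, plus 2 potassium-only draws | 9 | 2.1 |
| High risk, two-hourly after evidence of TLS | 24 | 9 | 2.7 |
| Daily minimum in protocol 5.4.2.1 | 12 | 6 to 7 | 1.7 to 2.0 |

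**Step 3: effect of the extra panels under an equal process.** If each panel had an independent chance p of producing a flag, the chance of at least one flag in k panels is 1 − (1 − p)^k. The values of p are assumptions.

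- p = 1%: 1 − 0.99^19 = 17.4% against 1 − 0.99^9 = 8.6%.
- p = 2%: 31.9% against 16.6%.

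A simulation of the two-analyte rule gave both arms the same four independent analytes, fluctuating around baseline with an assumed correlation time of 3 to 24 h. Flag rates, ACM against CM, were:

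- SD 8% of baseline: near 0 in both.
- SD 10%: 3-6% against 1-2%.
- SD 12%: 18-34% against 7-12%.
- SD 15%: 53-82% against 26-44%.

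The documents give no within-patient variability, so these rates show direction only.

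**Step 4: chance that a short episode meets a scheduled panel.** An episode of length L is seen if a panel falls within L hours of its onset.

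- L = 6 h, onset uniform over 168 h: ACM 102/168 = 61%, CM 54/168 = 32%.
- L = 6 h, onset uniform over 0-84 h: ACM 61.5/84 = 73%, CM 54/84 = 64%.
- L = 12 h, onset uniform over 0-84 h: ACM 79.5/84 = 95%, CM 100%. The ACM shortfall is the gap from 48 to 64.5 h in step 1.

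**Step 5: window against regimen.** ACM cytarabine starts on Day 6, at about 120 h, so the window closes 168 − 120 = 48 h into it. ACM mitoxantrone falls at about 120 + 72 + 12 = 204 h, outside the window. CM treatment is complete by about 86 h, well inside it.

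**Step 6: candidate remedies.** Cutting both arms at 86 h leaves ACM 12 against CM 9, still unequal. A grid at 12, 24, ..., 84 h gives 7 against 7. CM has a panel at every point. The nearest ACM panels are at 12, 24, 36, 48, 64.5, 76.5 and 88.5 h, all within 4.5 h.

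**The case against.** The strongest reply is that this is a descriptive table with limited consequences. The SAP's table templates remove p-values from safety summaries, and no decision rule rests on the TLS count. TLS is also reported through investigator-reported adverse events (SAP 7.11.2), which do not use the Table 8 rule. The CM schedule is a minimum, since the step-down to 12-hourly panels applies only without evidence of TLS and later tests may be added. Mandatory hydration, allopurinol and phosphate binder make a pure noise model unrealistic, and a noise crossing alone does not make clinical TLS. All of this stands, and it limits the importance of the point. It does not make the between-arm contrast interpretable, because objective 4 judges safety against CM.

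A reader might go further and infer that ACM must look worse by construction. The documents do not support that. Step 5 shows a feature that can lower the ACM count. Step 4 shows that the detection gap depends heavily on when episodes start and how long they last, and that it can reverse in the first 84 h.

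A reader might also infer that worst-value shift tables are compared between arms. SAP section 3 does define a shift table as a "two-way frequency table pairing baseline value with the most extreme post-baseline result", but section 7.11.4 specifies these tables within arm and by cycle (up to 10 weeks), and the template prints the arms separately. The 7-day panel counts do not describe them. What remains is a caution against reading the two arms' tables side by side.

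**Conclusion.** The point holds as an ascertainment problem. The planned between-arm TLS summary rests on about twice as many scheduled panels in ACM as in CM (19 against 9), and the SAP does not apply its own caveat to it. Confidence in the counts is high; they assume sampling at the scheduled minimum intervals. Under an equal process each added panel can only add cases, but the size of the effect rests on variability and episode timing that the documents do not give, and it may be close to zero. The net direction is open, and part of any observed difference may be a real drug effect. This is a cheap improvement to the analysis plan, not a flaw that undermines the trial.

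**What to change.** In SAP section 7.11.3 and the TLS summary table:

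- Keep the all-panel incidence for both arms.
- Add the number of panels per patient in the window, by arm.
- Add a between-arm comparison restricted to a common grid: the scheduled panel nearest each 12-h point from first dose to about 84 h, the end of CM mitoxantrone. State a tolerance and a rule for ties.
- Extend the section 7.11.4 caveat on unequal schedules to TLS, and to side-by-side reading of the within-arm shift tables.

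The sponsor should also reconcile protocol section 4.6.1.1 with section 5.4.2.1, which describes tumor lysis panels as daily at a minimum, so that the intended schedule is clear to the analyst.

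The cost is SAP wording, one derived flag and one extra table row; no new samples are needed. The downside is that the grid misses ACM events seen only on the denser post-infusion panels, and it stops before ACM cytarabine begins. It should therefore supplement the all-panel table and not replace it.

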7.11.4. Clinical Laboratory Parameters

Typical comparisons of results summarized by visit may have limited interpretability in this study because (1) study drugs from the two treatment arms are administered on

different cycle days (Days 1-9 for ACM versus Days 1-4 for CM), (2) the schedule for clinical laboratory evaluations (cycle day and frequency) is different between the treatment arms, and (3) additional cycles of treatment start according to patients' response to treatment rather than based on a predetermined schedule. Therefore, four groups of laboratory data will be summarized separately:

- Cycle 1 results (from all patients in the safety population) up to the day a patient starts Cycle 2 or 10 weeks after starting Cycle 1, whichever comes first
- Cycle 2 results (from patients in the safety population who receive at least 2 cycles of study drug) up to the day a patient starts Cycle 3 or 10 weeks after starting Cycle 2, whichever comes first
- Cycle 3 results (from patients in the safety population who receive at least 3 cycles of study drug) up to the day a patient starts Cycle 4 or 10 weeks after starting Cycle 3, whichever comes first
- Cycle 4 results (from patients in the safety population who receive 4 cycles of study drug) up to 10 weeks after starting Cycle 4

Laboratory test results measured on a continuous scale and changes from baseline values will be summarized within treatment arm using mean, standard deviation, median, minimum and maximum values. Results will be summarized at baseline, on Days 1-9, and every 7 days starting with Day 15 for patients receiving ACM, and at baseline, on Days 1-4, and every 7 days starting with Day 8 for patients receiving CM. Up to the point of starting a new treatment cycle or withdrawing from the study, a patient's most recent test result will be carried forward and included in analyses on days when clinical laboratory testing was not performed.

Ordinal categorical test results will be summarized within treatment arm using shift tables. Additionally, for tests where CTCAE [version 4.03] severity criteria are specified, CTCAE severity grades will be summarized in shift tables.

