5.4.4 Cycle 1 – At Hematologic Recovery

- Assess response by bone marrow biopsy and/or aspiration at time of hematologic recovery (ie, absolute neutrophil count (ANC) >1000 μ L and platelet count >100,000 μ L) or Day 45 (\pm 2), whichever occurs first. If the bone marrow biopsy and/or aspirate is nonproductive or not diagnostic, the procedure must be repeated within 7 days.
 - At time of response assessment, 6 to 8 bone marrow slides will be prepared and sent to the Sponsor. Details regarding the collection and shipping of these slides is provided in the Study Manual.
- Assess for AEs, including tumor lysis clinical symptoms
- Record only those medications (prescription, nonprescription, nutritional supplements) administered in conjunction with an AE.

5.4.5 Cycles 2 - 4

Patients who achieve CR, CRi, CRp, or PR after the first cycle (completion of all doses) may receive up to 3 additional optional cycles of treatment. After completing the first cycle of treatment, continued use of mitoxantrone is optional. Mitoxantrone must be omitted from subsequent cycles if the patient's lifetime daunorubicin equivalent exceeds 460 mg/m² (see *Appendix G* for conversion table) or the LVEF drops below 45%.

Patients not demonstrating evidence of CR, CRi, CRp, or PR after the first cycle of treatment will be considered for removal from the study, although with permission of the Medical Monitor, induction treatment may continue if clinically indicated and provided there is no evidence of toxicity \geq NCI CTCAE grade 4.

However, patients randomized to CM with progressive disease or no response after 1 cycle of CM may cross over to receive ACM. In addition, patients randomized to CM with the best response of a PR after 2 cycles of CM may also cross over to receive ACM. Patients who cross over to ACM may receive up to a combined total (CM + ACM) of 4 cycles.

There is a maximum limit of 90 days between the start of cycles unless otherwise discussed with the medical monitor.

5.4.5.1 Cycles 2 - 4, Day 1 – Within 10 Hours Prior to First Dose

Perform the following assessments in patients receiving subsequent cycles of chemotherapy:

- *If clinically indicated*, administer pretreatment IV hydration, oral allopurinol, and oral phosphate binder (see *Section 4.6.1*)

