5.4.5.2 Cycles 2 - 4, Day 1 – Just Prior to First Dose

Perform the following procedures just prior to dosing on Day 1:

- Physical examination including weight (kg) for recalculation of BSA
- Record vital signs measured 5-15 minutes prior to the initiation of infusion following a 5-minute rest
- Assess ECOG PS (*Appendix B*)
- Collect blood for evaluation of laboratory parameters (*Appendix D*):
 - Hematology
 - Tumor lysis labs
 - Fibrinogen level (only required if clinically indicated)
- If supportive care measures for prevention of tumor lysis were initiated, monitor urine output **frequently** to ensure that it equals fluid input. If input is greater than output by 10%, administration of diuretics is encouraged. Replacement of excessive fluid losses, including from diarrhea, should be done unless otherwise clinically indicated.

- Collect urine or serum sample for β -hCG pregnancy test for females of child-bearing potential
- Record only those medications (prescription, nonprescription, nutritional supplements) administered in conjunction with an AE.

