PBSC	Peripheral Blood Stem Cells
PFS	Progression-Free Survival
PH	Proportional Hazards (model)

* The term CRp appears in this document to maintain compatibility with the study's case report forms, however CRp will not be used by the hematologists performing the central review of patients' responses and it is not expected to be used by the investigators.

PR	Partial Remission
PT	(MedDRA) Preferred Term
RFS	Relapse-Free Survival
ROC	Receiver Operating Characteristic (curve)
SAE	Serious Adverse Event
SAP	Statistical Analysis Plan
SCT	Stem Cell Transplant/Transplantation
SMQ	Standardized MedDRA Query
SOC	(MedDRA) System Organ Class
TEAE	Treatment Emergent Adverse Event
TLS	Tumor Lysis Syndrome
WHO	World Health Organization

3. Definitions

Standard statistical terminology (e.g., type-1 error rate and significance level) is omitted intentionally. Efficacy endpoints are defined in Section 4.1 below (see Table 1).

Baseline Value: last measured value prior to the first dose of study drug (or prior to randomization for patients not treated)

Combined CR: response assessment of CR, CRi or CRp

Combined Remission: response assessment of CR, CRi, CRp or PR

Crossover Patient: a patient randomized to CM who, following 1-2 cycles of CM, receives ACM as stipulated in the study protocol

Cycle 1: period of time from the first dose of study drug until the start of study drug in cycle 2 or the start of alternative AML therapy other than supportive measures such as blood product transfusions (hence a patient whose first response assessment in cycle 1 is a CRi or CRp is considered to have achieved CR if neutrophils and platelets recover prior to initiation of cycle 2 or alternative AML therapy)

Cycle-1 Combined CR Rate: percentage of patients who achieve a combined CR (CR, CRi or CRp) after one cycle of treatment

Cycle-1 Combined Remission Rate: percentage of patients who achieve a combined remission (CR, CRi, CRp or PR) after one cycle of treatment

Cycle-1 CR Rate: percentage of patients who achieve a CR after one cycle of treatment (see section 7.9.1)

Intent-to-Treat Population: all patients randomized to receive study drug regardless of whether they actually received study drug and regardless of whether evidence is found indicating they failed to meet study inclusion/exclusion criteria or had other protocol violations (see section 7.1)

Neutrophil Recovery: Absolute neutrophil count $\geq 1 \times 10^9/L$ following the administration of study drug

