In general, data values will be obtained directly from the clinical database (e.g., birth date, treatment dates, AML relapse date and death date). Derivations for certain values not collected explicitly in the database are explained in relevant sections below (e.g., age and treatment failure date, sections 7.7 and 7.9.2, respectively). In some instances, it is beyond the scope of this SAP to explain schemes for patient classifications and data derivations (e.g., classifying patients in cytogenetic risk group according to published criteria). These details will be expounded in the clinical study report.

Durations of time expressed in months (e.g., times-to-event endpoints) will be reported in proportional “months” according to the formula

$$\text{months} = \frac{12}{365.25} \times \text{days}$$

Baseline value of a characteristic is defined as the last measured value prior to the first dose of study drug (or prior to randomization for patients not treated).

Statistical p-values will be truncated for display at the third digit following the decimal point. P-values less than 0.001 will be displayed as “<0.001.”

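### SAP 7.11.4 measures Cycle 2–4 laboratory changes from the pre-Cycle 1 value and closes each cycle group at 10 weeks, so the by-cycle tables can understate later falls and omit late results.

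*SAP*

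**What the plan says.** **Baseline.** SAP section 3 defines it once, as the "last measured value prior to the first dose of study drug (or prior to randomization for patients not treated", and section 7 repeats the definition: "Baseline value of a characteristic is defined as the last measured value prior to the first dose of study drug". The first dose is the one that opens Cycle 1, since section 3 defines Cycle 1 as the "period of time from the first dose of study drug until the start of study drug in cycle 2". Section 7.11.4 gives no other reference for Cycles 2–4.

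**Groups.** Section 7.11.4 forms one group per cycle and summarizes each separately. The Cycle 1 group takes results "up to the day a patient starts Cycle 2 or 10 weeks after starting Cycle 1, whichever comes first". Cycles 2 and 3 follow the same rule, and Cycle 4 stops at 10 weeks. The section then says: "Laboratory test results measured on a continuous scale and changes from baseline values will be summarized within treatment arm". Within each group, values and changes are tabulated daily over the dosing days and then weekly. In the same section, the last result is carried forward until a new cycle starts or the patient withdraws; the 10-week limit is not mentioned.

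**Shift tables.** Section 3 defines one as a "two-way frequency table pairing baseline value with the most extreme post-baseline result". The Appendix 2 template is headed by the worst score or grade during the study. Neither is split by cycle.

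**Protocol.** On spacing, section 5.4.5 says: "There is a maximum limit of 90 days between the start of cycles unless otherwise discussed with the medical monitor". Post-treatment laboratory draws are weekly, with no stated last day (5.4.5.5). Just before dosing in Cycles 2–4, section 5.4.5.2 requires sites to "Collect blood for evaluation of laboratory parameters", covering hematology and tumor lysis labs; Stage 1 has the same rule (5.3.5.2). After screening, the Appendix A visit schedules show the full chemistry panel only at End of Study.

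**The concern.** By-cycle tables are there to show what each cycle does to the patient. Inclusion criterion 2 requires more than 5% marrow blasts, and no eligibility criterion sets a minimum platelet or neutrophil count, so Cycle 1 can begin with disease-depressed counts. Patients continue mainly after CR, CRi, CRp or PR. A responder in CR enters Cycle 2 with platelets of about 100,000/µL or more and neutrophils of about 1,000/µL or more, as CR requires. Subtracting the pre-Cycle 1 count from a Cycle 2 count then credits the earlier remission to the later cycle.

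The 10-week end point is a separate problem. It removes results from patients whose next cycle is delayed, who may include those slow to recover, and from anyone followed for longer than 10 weeks after starting the last cycle. The panel most exposed is full chemistry: tumor lysis labs (Protocol Appendix D) contain no ALT, AST or alkaline phosphatase. If End of Study falls late, the only post-baseline full panel in the visit schedule is missing from the by-cycle value and change summaries.

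**Working it through.** The plan states no figure here to reproduce. The check is one identity and some date arithmetic.

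**1. Effect of the reference value**

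Let B1 be the value before Cycle 1, Bk the value before Cycle k, and Nk a value during Cycle k.

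- Change under the SAP: Nk − B1
- Change over the cycle itself: Nk − Bk
- Difference: (Nk − B1) − (Nk − Bk) = Bk − B1

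The SAP change therefore understates a fall whenever Bk > B1, and by exactly Bk − B1. It becomes positive only if Nk > B1. If Bk < B1, it overstates the fall.

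The documents give no patient counts, so the platelet values below (×10⁹/L) are assumptions. B2 is set at 120, compatible with CR.

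| B1 | N2 | SAP change (N2 − B1) | Change over Cycle 2 (N2 − 120) |
|---|---|---|---|
| 20 | 10 | −10 | −110 |
| 20 | 25 | +5 | −95 |
| 20 | 40 | +20 | −80 |
| 75 | 25 | −50 | −95 |
| 150 | 25 | −125 | −95 |

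With B1 from 20 to 150 and N2 from 10 to 40, the SAP change runs from 10 − 150 = −140 to 40 − 20 = +20. The change over Cycle 2 runs from −110 to −80.

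**2. Effect of the 10-week end**

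- 10 weeks = 70 days. The spacing limit is 90 days, extendable.
- Uncovered: 90 − 70 = 20 days, or 20/90 = 22% of a 90-day interval.
- Over three such intervals: 3 × 20 = 60 days.
- With Day 1 as cycle start, the group closes at Day 71. The weekly grid (from Day 15 for ACM, Day 8 for CM) reaches Day 71 in both arms, then Days 78 and 85, which fall outside.
- If the next cycle starts by Day 71, nothing between those two cycles is lost.
- After the last cycle there is no next start, so every result after Day 71 falls outside, including a late End of Study sample.

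**3. Consistency within 7.11.4**

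Carry-forward runs to the next cycle or withdrawal, but the group it feeds closes at 10 weeks. For a patient with a 90-day interval the two rules disagree about Days 78 and 85.

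**The case against.** The case for leaving the section alone has real substance.

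- **Absolute values are in the same tables.** Each group tabulates values from Day 1 of the cycle, and hematology is drawn on Day 1 before dosing, so a reader can see the starting level and the fall. Listings by patient are also planned (SAP 7.11). This stands: the distortion is confined to the change columns.
- **Shift tables look study-wide.** A reader might infer that late results reach no table at all, or that Cycle 2–4 shift tables will show improvement. The documents do not support either inference. The section 3 definition and the Appendix 2 template carry no cycle or 10-week limit, so late results probably enter, and there may be no separate later-cycle shift table. But 7.11.4 does not say whether its shift tables follow the four groups, and a study-wide worst grade cannot show what a later cycle did.
- **Crossover.** A reader might infer that the first ACM cycle after CM is badly misjudged. Most crossover routes require progression or no response after CM (Protocol 4.5.3.4), so recovery into remission largely does not apply there.
- **The 20 days are a ceiling.** Marrow is assessed at recovery or about Day 45, and many next cycles may start within 10 weeks. The treatment-emergent window also ends 30 days after the last dose, about Day 39 for ACM (9 + 30) and Day 34 for CM (4 + 30) in a single cycle. Both points limit the size; neither explains closing the laboratory group while weekly draws continue.
- **Chemistry.** The overall design section (Protocol 4.1) speaks of chemistries daily in hospital and weekly afterward, without naming a panel. The visit schedules list only tumor lysis labs at those times. The statement about full chemistry therefore rests on the visit schedules.
- **Resetting baseline has a cost.** If the pre-cycle value replaced the study baseline, toxicity left over from Cycle 1 would become the new normal. This is a sound reason to add a reference and not to replace one.

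Adverse event tables do not close the gap. A laboratory abnormality is recorded as an AE only with clinical sequelae or an intervention (Protocol 8.4), and the planned AE tables are not split by cycle.

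**Conclusion.** The point holds as a defect in descriptive safety tables; efficacy inference is not affected. For hematology, the Cycle 2–4 change columns differ from the cycle's own change by the pre-cycle value minus the pre-Cycle 1 value. In the assumed CR example with platelets of 20 before Cycle 1 and 120 before Cycle 2, that is 100 × 10⁹/L. A reported gain is possible but conditional. It would be too strong to say that later-cycle toxicity generally appears as improvement.

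The 10-week end leaves up to 20 days of a 90-day interval, and all results more than 10 weeks into the last cycle, outside the by-cycle value and change tables. It also conflicts with the carry-forward rule. The 22% is an upper limit within a 90-day interval, not an expected loss, and it would be larger only where the spacing limit is extended. How many patients are affected cannot be derived from the documents.

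The conclusion assumes that section 3's baseline applies to every cycle group, as nothing in 7.11.4 says otherwise, and that shift tables are study-wide. If they follow the four groups, both problems extend to them. The change is worth making before the tables are programmed.

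**What to change.** In SAP 7.11.4:

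1. Keep the pre-Cycle 1 baseline and the change from it, so that cumulative toxicity stays visible.
2. For the Cycle 2, 3 and 4 groups, add the change, and the CTCAE grade shift, from the last value before the first dose of that cycle. Where a test is not drawn just before the cycle, use the last available value.
3. End each group at the start of the next cycle or, if there is none, at the End of Study assessment. This also brings the group into line with the carry-forward rule.
4. State whether shift tables are study-wide or per cycle.

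Apply the same group end to vital signs in 7.11.5, which reuses these groups. The leukemic-baseline argument does not extend to vital signs, so they need no added reference on that ground.

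The cost is SAP wording and programming, extra table columns, and sparse late time points that should be read with their patient counts. No new data are needed, because pre-dose hematology and tumor lysis labs are already collected in every later cycle. The SAP still names Amendment 7 as current and promises review after later amendments, while the protocol describes Amendment 11, so a revision is due in any case.
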